**Novexatin 10% topical solution**

**Protocol / Study No. NVXT 1404/71442603**

1. Analysis will be performed also including patients without an assessment at Day  $365 \pm 14$ . Patients with missing data at Day  $365 \pm 14$  will be considered therapeutic failures.
2. Analysis will be performed also including patients without an assessment at Day  $365 \pm 14$ . Patients in Group C with missing data at Day  $365 \pm 14$  will be treated as therapeutic successes and patients from the Groups A and B with missing data at Day  $365 \pm 14$  will be treated as therapeutic failures.

Similar sensitivity analyses will be conducted including patients without an assessment at Day  $141 \pm 7$  for the 4th comparison in the hierarchical, conditional-stepwise evaluation scheme.

#### **8.2.2 Treatment-by-Site Interaction and Pooling of Clinical Sites**

As this is a multiple-site study, the interaction of treatment-by-site may be evaluated for superiority testing by the Cochran-Mantel-Haenszel test (stratified by site) using Breslow-Day test for the primary efficacy endpoint at the 5% significance level ( $p < 0.05$ , 2-sided) in the ITT population. A site(s) with a low enrollment rate(s) may be pooled with its geographically closest site, so as to avoid bias in the stratification of the sites in the CMH test and in the estimation of a treatment-by-site interaction effect. The pooling will be done for low enrolling sites that account for less than 4-7% of the total number of patients in the ITT population at the site with the highest enrolling rate. If no treatment-by-site interaction is identified with the primary endpoints then no adjustment will be made to any efficacy analysis.

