10.2 Determination of Sample Size

The primary statistical analysis of interest is a comparison of the rates of therapeutic cure (as defined by "clinical cure" AND "mycological cure") of Novexatin® 10% topical solution to the rate of therapeutic cure of placebo in the Intent-to-Treat Population (ITT). The rate of therapeutic cure for the Novexatin® 10% topical solution 8-week regimens is expected to be approximately 49%. The rate of therapeutic cure for placebo is expected to be approximately 21%. Approximately 46 patients in each treatment group in the ITT population will provide over 80% power to show a difference at $p < 0.05$ (two-sided Z test and a pooled response rate for the standard error of the difference in proportions) between each of the active treatment groups and the placebo group. To allow for a 23% drop-out rate, a total of 180 patients will be enrolled in the study, with up to 60 patients in each of the treatment groups.

A Randomized, Placebo-Controlled, Double-Blind, Parallel-Group, Multi-Site Phase 2b Clinical Study to Assess the Efficacy, Safety and Tolerability of 8-Week Regimens of Novexatin®, 10% Topical Solution (Taro Pharmaceuticals, USA, Inc.) in Patients with Mild to Moderate Onychomycosis

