**Novexatin 10% topical solution**

**Protocol / Study No. NVXT 1404/71442603**

**4. RANDOMIZATION AND BLINDING**

The study product will be packaged and blinded by an independent clinical packaging company. The randomization will be generated in blocks of 3, containing the study products in three configurations:

- A. bottles #1 & 2 – Test and bottles #3 & 4 – Placebo
- B. bottles #1 & 2 – Test and bottles #3 & 4 – Test
- C. bottles #1 & 2 – Placebo and bottles #3 & 4 – Placebo.

Three patients worth of study product bottles 1 & 2 will be packed into a larger box. This larger box will be designated “one block” of study product. The study product bottles 1 & 2 will be blinded, packaged and delivered to the study site in blocks at the beginning of the enrollment. Bottles 3 & 4 will be delivered to the study site before Visit 5 (2nd treatment start).

At each Visit 2 and Visit 5 each patient will receive two 5 ml bottles of study product according to the randomization code. Patients will be randomized to a treatment regimen in a blinded fashion by assigning randomization numbers in ascending sequential order starting with the lowest available randomization number at each site. All patients randomized will be identified by initials, date of birth, and a unique six-digit patient number. The first two-digits will identify the Investigator site where the patient was enrolled and the last four will correspond with the randomization number of study product bottle assigned to the patient. A perforated or two-part label will be attached to each of the small sized boxes of study product supplies. Both pieces of the label will include the following information: Protocol number, randomization number, space for patient’s initials, statement that the study product is for investigational use only, space for dispensing date and the Sponsor’s name. In addition all patients will be provided with written instructions on how to use the study product. One part of the label shall remain attached to the box. The other part will be removed prior to dispensing and attached to the study product log.

The Investigator, staff at the study site, study monitors, and data analysis/management personnel will be blinded to the patient assignment.

At the end of the study, after all the clinical data has been entered and the study database has been locked, a copy of the randomization will be sent to the statistician.

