Statistical testing will begin with comparison 1. If statistical significance is attained with comparison 1 ( $p < 0.05$ ), then a claim of superiority for comparison 1 can be made and the next comparison in the hierarchical evaluation scheme can be tested for statistical significance. If statistical significance is not attained for comparison 1 ( $p \geq 0.05$ ), then testing of all subsequent comparisons is stopped. The hierarchical, conditional-stepwise evaluation scheme allows for each comparison to be evaluated at the 5% level, while preserving an overall type I error rate of no more than 5%. For the proportion of patients in each treatment group with a complete and almost complete therapeutic cure, complete and satisfactory clinical cure and mycological cure of onychomycosis of the target toenail, the statistical analysis for superiority will be conducted using a two-sided Cochran-Mantel-Haenszel (CMH) exact test, stratified by clinical site, at the 5% significance level. The primary and secondary analyses will be performed using an observed case (OC) analysis in the ITT population. Patients discontinued because of lack of treatment effect will be included in the primary analysis as treatment failures.

The following two sensitivity analyses will also be performed on the primary efficacy endpoint in the hierarchical, conditional-stepwise evaluation scheme:

**NOVUM PHARMACEUTICAL RESEARCH SERVICES  
STATISTICAL ANALYSIS PLAN**

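### The site-pooling rule in SAP 8.2.2 is a percentage range of the largest site's count, so the strata of the primary exact CMH test are not fixed and in many layouts no small site would be pooled

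*SAP*

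**What the plan says.** SAP 8.2.1 makes each efficacy comparison a "two-sided Cochran-Mantel-Haenszel (CMH) exact test, stratified by clinical site, at the 5% significance level". SAP 8.7 records this as a replacement for the protocol's unstratified Z test. SAP 8.2.2 then deals with small sites: "A site(s) with a low enrollment rate(s) may be pooled with its geographically closest site". The stated aim is to avoid bias in the site stratification and in the interaction estimate. Two sentences in 8.2.2 govern this. The first makes pooling optional. The second says it will be carried out for low-enrolling sites with "less than 4-7% of the total number of patients in the ITT population at the site with the highest enrolling rate". The section does not choose a value within the range, and does not say how or when one is to be chosen. Neither document gives the number or size of sites.

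Three other provisions bear on this. On allocation, SAP section 4 says "The randomization will be generated in blocks of 3", so a site that completes a single block has one patient per group. SAP 8.2.1 analyses observed cases. Protocol 10.2 allows for 23% dropout and justifies the sample size with a "two-sided Z test and a pooled response rate for the standard error of the difference in proportions".

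**The concern.** A programmer cannot apply a cut-off stated as a range. Because the strata define the test, the p-value for Group B versus Group C at Day 365 depends on a choice that the plan leaves open. That comparison is the gate to all later ones in the hierarchy.

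The percentage also has a small base: the largest site, not the trial. In an exact conditional CMH test a stratum adds nothing if one of the two compared groups has no observed patient, or if every outcome in it is the same. If small sites stay separate, part of the data carries no weight in the test, and the rule misses its own purpose.

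**Working it through.** **1. The plan's own sample size.** Inputs from protocol 10.2: 49% versus 21%, two-sided 5%, pooled Z test, 46 per group, 23% dropout.

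- Pooled term: mean rate 0.35, √(2 × 0.35 × 0.65) = 0.6745.
- Unpooled term: √(0.49 × 0.51 + 0.21 × 0.79) = 0.6448.
- Power at 46 per group: Φ[(0.28 × √46 − 1.96 × 0.6745) / 0.6448] = Φ(0.895) = 81%.
- Dropout: 46 / 0.77 = 59.7, so 60 per group.

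The stated figures are reproduced, for an unstratified Z test.

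**2. The literal cut-off.** It is 0.04 × L to 0.07 × L, where L is the ITT count at the largest site. L is not in the documents and is assumed here.

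| L | 4% | 7% | Largest site size pooled (4% / 7%) |
|---|---|---|---|
| 10 | 0.40 | 0.70 | none / none |
| 15 | 0.60 | 1.05 | none / 1 |
| 30 | 1.20 | 2.10 | 1 / 2 |
| 45 | 1.80 | 3.15 | 1 / 3 |
| 60 | 2.40 | 4.20 | 2 / 4 |

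For a site of 3, the 7% reading needs L of at least 43 (0.07 × 43 = 3.01). The 4% reading needs L above 75 (0.04 × 75 = 3.00, which is not above 3). With L of 14 or fewer, no site can be pooled under either reading.

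**3. The choice within the range can decide everything.** Take one site of 60 and 40 sites of 3 (60 + 120 = 180). At 4% the cut-off is 2.4 and no site is pooled. At 7% it is 4.2 and all 40 are. Simulated power is 69.6% at 4% and 78.5% at 7%.

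**4. How often a one-block site counts.** For B versus C both patients must be observed and their outcomes must differ: 0.77² × (0.49 × 0.79 + 0.51 × 0.21) = 0.5929 × 0.4942 = 0.29. Such a site is informative 29% of the time.

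**5. Power with sites left separate.** Simulation for B versus C: 180 randomised in blocks of 3, 23% dropout, no site effect, exact conditional CMH, 1,500 runs per setting (Monte Carlo error about 1 point). For reference, the unstratified Z test has about 82% and the unstratified exact test about 78%. The SAP rule pools no site in any of these layouts.

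| Assumed layout | Observed B and C patients in non-informative strata | Power |
|---|---|---|
| 6 sites of 30 | 0.2% | 77% |
| 12 of 15 | 4% | 77–78% |
| 20 of 9 | 15% | 75% |
| 30 of 6 | 30% | 73% |
| 30, 20, 10 and 40 of 3 | 42% | 69% |
| 60 of 3 | 62% | 62% |

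**6. What pooling recovers.** A separate simulation compared unpooled sites with strata of at least 5 per treatment group, with no site effect.

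| Assumed layout | Unpooled | Pooled | Gain |
|---|---|---|---|
| 20 of 9 | 74% | 76% | 2 |
| 30 of 6 | 73% | 79% | 6 |
| 30, 21, 9 and 40 of 3 | 69% | 77% | 8 |
| 60 of 3 | 60% | 77% | 17 |

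A further run of 6,000 replicates, with 10 strata of 6 randomised per group, agrees for the two equal layouts: 75.2% to about 77% for 20 sites of 9, and 72.4% to about 77% for 30 of 6.

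**The case against.** The strongest counter-case is that the documents give no site numbers, so every power figure is conditional, and that the gains assume no site effect although SAP 8.7 stratifies precisely because sites may differ. Pooling to 5 strata was simulated with site variability on the logit scale. At a standard deviation of 0.7, unpooled versus pooled power was 71.7% versus 71.5% (20 sites of 9) and 69.7% versus 71.8% (30 of 6). At 1.0 it was 68.2% versus 66.0% and 65.4% versus 65.0%. So the gain shrinks and can reverse slightly.

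This stands in part. Five strata of 12 randomised per group are coarser than a minimum of 5 per group. With that minimum and a standard deviation of 1.0, power is level for the two equal layouts and still higher with pooling for the two sparser ones.

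Four stronger readings are tempting, and the documents do not support them:

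- *Almost no site is ever pooled.* With a largest site of 45 to 60 and the 7% reading, every site of up to 3 or 4 patients is pooled.
- *Patients in small sites are lost.* Only non-informative strata add nothing to the test. SAP Table V still reports counts and proportions for all observed cases.
- *The pooling rule is why power falls below 80%.* About 4 points (82% to 78%) come from using an exact test at all, and pooling cannot recover them.
- *The percentage refers to the whole ITT population.* That would give a workable 5.5 (0.04 × 138) to 12.6 (0.07 × 180) patients, but the wording ties it to the highest-enrolling site.

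**Conclusion.** The textual defect holds without any assumption: the cut-off is a range, pooling is both optional and definite, and the strata of the gating primary test are therefore open. It also follows from the wording that a one-block site stays separate unless the largest site is big for a trial of 180.

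The power cost is conditional on an unknown site layout. It is negligible with sites of about 15 or more. With 20 to 30 equal sites and no site effect it is about 2 to 6 points, shrinking to none with large site variability. With many one-block sites it is 8 to 17 points with no site effect. This should be corrected before unblinding. It does not show that the trial is underpowered.

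**What to change.** Replace the range in SAP 8.2.2 with one mandatory absolute threshold on total patients per site. A threshold per treatment group would not work, because under SAP section 4 the statistician receives the randomization only after database lock, so group counts by site are not available blinded.

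For example: any site with fewer than 15 patients with a Day 365 assessment (about 5 per group under 1:1:1) is combined with its nearest site, smallest first, until each stratum reaches 15. Counting assessed patients rather than all ITT patients matches the observed-case analysis. Change the optional wording so that pooling is required, fix the strata before unblinding, and use the same strata in every efficacy test.

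The simulated rule was a minimum of 5 per group. The total-count version is its blinded counterpart and was not simulated itself, so the gains above are a guide. The cost is a short rewording of SAP 8.2.2 and slightly coarser control for site.

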#### **8.2.3 Additional Analyses**

In addition to the efficacy statistical analyses specified in the protocol, the analyses described in Section 8.2.1 above, including sensitivity analyses, will also be performed using the following endpoints:

1. Primary endpoint (complete therapeutic cure) with Canfield's evaluation for % toenail involvement.
2. Secondary endpoint #1 (complete or almost complete therapeutic cure) with Canfield's evaluation for % toenail involvement for complete cure in addition to the current evaluation for almost complete cure by Canfield's evaluation.
3. Secondary endpoint #3 (complete clinical cure) with Canfield's evaluation for % toenail involvement for complete cure.

Patients will only be included in analyses 1, 2 and 3 above if they meet inclusion criterion #6 (Mild to moderate severity at Visit 1 as defined by Investigator's estimation of approximately

**NOVUM PHARMACEUTICAL RESEARCH SERVICES**  
**STATISTICAL ANALYSIS PLAN**

**Novexatin 10% topical solution**

**Protocol / Study No. NVXT 1404/71442603**

10% to 35% toenail involvement) on the basis of Canfield's evaluation to define mild to moderate severity instead of by Investigator's estimation.

### **8.3 Safety Analysis**

All study patients who are randomized to the active treatment period of the study, and received study product will be included in the comparative safety analysis. The safety profile of each treatment group will be evaluated by comparing adverse events, application site reactions, vital signs and changes in clinical laboratory results obtained throughout the study. Data will also be collected during the study to compare the results of the KOH stains to the mycological culture results observed during the study.

#### **8.3.1 Adverse Events**

All the adverse events (AEs) reported throughout the study will be coded and classified according to the MedDRA (Medical Dictionary for Regulatory Activities) coding dictionary (Version 19.0 or higher). Each adverse event is to be evaluated for date of start and end, seriousness, severity, causal relationship with the study drugs, action taken and outcome.

All AEs will be listed by treatment group and patient.

A summary table of the number and percent of patients with AEs by system organ class, preferred term, and treatment will be presented. Each patient will be counted only once within each preferred term. Other summaries may be added based on the obtained data.

A frequency summary table of the number of AEs by system organ class, preferred term, severity, and treatment will be presented. Severity will be classified as "Mild", "Moderate", or "Severe".

Similarly, a frequency summary table of the number of AEs by system organ class, preferred term, and relationship to a study drug, and treatment will be presented. Relationship to a study drug will be classified as "Not Related" or "Related" where "Related includes "Possible", "Probable", or "Definite".

Should sufficient data exist, adverse event frequencies will be compared between treatments using Fisher's exact test. If the global Fisher's exact test is statistically significant among the three treatment groups at the 5% alpha level (i.e.,  $p < 0.05$ ), then Fisher's exact test using only the Group A and Group B may be performed to identify any potential statistically significant differences that are clinically relevant between the two active treatment groups over the period from Day 1 to Day  $141 \pm 7$  days (i.e., following completion of the first 8 weeks of treatment when both groups have the same test treatment regimen) and over the study duration from Day 1 to Day  $365 \pm 14$  days.

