**2. OBJECTIVES**

1. Determine the rates of complete therapeutic cure of Novexatin® 10% topical solution (Taro Pharmaceuticals, USA) after daily dosing for one 8-week treatment period (Treatment Group A) and two 8-week treatment periods separated by a 32-week rest period (Treatment Group B), and Placebo (vehicle) topical solution (Taro Pharmaceuticals, USA) after two 8-week treatment periods separated by a 32-week rest period (Treatment Group C), at three test-of-cure visits (Day 141, Day 281 and Day 365) in patients with mild to moderate distal subungual onychomycosis of the target toenail.
2. Compare rates of complete therapeutic cure between Treatment Groups according to a hierarchical evaluation scheme detailed in the statistical sections.
3. Evaluate safety and tolerability of the two regimens of Novexatin® 10% topical solution (Treatment Groups A and B) in patients with mild to moderate distal subungual onychomycosis of the target toenail.

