**Novexatin 10% topical solution**

**Protocol / Study No. NVXT 1404/71442603**

topical solution (Taro Pharmaceuticals USA) for the treatment of mild to moderate distal subungual onychomycosis of the target toenail. Additionally the active formulation in these regimens will be assessed for superiority to a placebo topical solution.

Up to 180 eligible patients with distal subungual onychomycosis who meet all the inclusion criteria and none of the exclusion criteria will be randomized into the study at Visit 2. Patients must be at least 18 years of age, in overall good health. They should have a current diagnosis of distal subungual onychomycosis of mild-moderate severity. Before any study-specific procedures are performed all patients will read and sign the IRB-approved informed consent form.

At least 60 qualified patients in each treatment group will receive randomized and blinded study product. The randomization scheme will be 1:1:1 (Active Treatment A: Active Treatment B: Placebo C). The study products are:

**Test:** Novexatin® 10% Topical Solution (Taro Pharmaceuticals, USA)

**Placebo:** Placebo (Vehicle) Topical Solution (Taro Pharmaceuticals, USA)

Patients will be assigned to one of the three treatment groups:

**Treatment Group A:** Test treatment for Days 1 – 56 and Placebo treatment for Days 281 – 336

**Treatment Group B:** Test treatment for Days 1 – 56 and Days 281 – 336

**Treatment Group C:** Placebo treatment for Days 1 – 56 and Days 281 – 336

Treatment and study durations will be as follows:

**Study Duration:** 365 days (52 weeks)

Patients will undergo evaluation for clinical and mycological cure of onychomycosis at the 7 clinic visits as per study schematic. Randomized patients who withdraw from the study will not be replaced. The study will be conducted according to the following schedule:

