# P-value will not be presented if the preceding one is  $\geq 0.05$ .

Treatment Group A: Novexatin® 10% Topical Solution for Days 1 – 56 and Placebo (Vehicle) Topical Solution for Days 281 – 336

Treatment Group B: Novexatin® 10% Topical Solution for Days 1 – 56 and Days 281 – 336

Treatment Group C: Placebo (Vehicle) Topical Solution for Days 1 – 56 and Days 281 – 336

Source: Listing L16.2.6.5.1, adeff  
Created on: ddmmmyy hh:mm

Page 1 of N

**T14.3.1.1 Summary of Frequency of All Adverse Events by Body System: Day 1 to Day 141 ± 7  
(Safety Population)**

| Body System                   | MedDRA Term | Treatment Group A
(N = xxx) |                  | Treatment Group B
(N = xxx) |                  | Treatment Group C
(N = xxx) |                  | Fisher's
p-value |
|-------------------------------|-------------|--------------------------------|------------------|--------------------------------|------------------|--------------------------------|------------------|---------------------|
|                               |             | Events                         | Patients
n(%) | Events                         | Patients
n(%) | Events                         | Patients
n(%) |                     |
| Patients with at least one AE | Total       | xx                             | xx (xx.x)        | xx                             | xx (xx.x)        | xx                             | xx (xx.x)        | x.xxxx              |
| Ear and labyrinth disorders   | Ear pain    | xx                             | xx (xx.x)        | xx                             | xx (xx.x)        | xx                             | xx (xx.x)        | x.xxxx              |
|                               | etc.        |                                |                  |                                |                  |                                |                  |                     |

Treatment Group A: Novexatin® 10% Topical Solution for Days 1 – 56 and Placebo (Vehicle) Topical Solution for Days 281 – 336

Treatment Group B: Novexatin® 10% Topical Solution for Days 1 – 56 and Days 281 – 336

Treatment Group C: Placebo (Vehicle) Topical Solution for Days 1 – 56 and Days 281 – 336

Source: Listing L16.2.7.1

Created on: ddmmmyy hh:mm

Page 1 of N

**T14.3.1.2 Summary of Frequency of All Adverse Events by Body System: Day 1 to Day 365 ± 14  
(Safety Population)**

**T14.3.2 Summary of Frequency of All Adverse Events by Relationship  

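### No adverse event table is limited to the second course, the only period in which regimens A and B differ, and the full-year patient counts do not register recurrence

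*SAP*

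**What the plan says.** SAP section 3 gives Group A as "Test treatment for Days 1 – 56 and Placebo treatment for Days 281 – 336" and Group B as "Test treatment for Days 1 – 56 and Days 281 – 336". SAP section 2 lists as the third objective: "Evaluate safety and tolerability of the two regimens of Novexatin® 10% topical solution (Treatment Groups A and B".

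SAP 8.3.1 plans the number and percent of patients with AEs by system organ class and preferred term, with the rule "Each patient will be counted only once within each preferred term". If a three-group Fisher test is significant, "then Fisher's exact test using only the Group A and Group B may be performed", over two windows. The first runs to Day 141, described as "following completion of the first 8 weeks of treatment when both groups have the same test treatment regimen". The second is "over the study duration from Day 1 to Day" 365.

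The shells follow these windows: T14.3.1.1 covers Day 1 to 141, and the other is "T14.3.1.2 Summary of Frequency of All Adverse Events by Body System: Day 1 to Day 365". The T14.3.1.1 shell, printed for both, shows Events, Patients n(%) and a Fisher p-value. T14.3.2 (relationship), T14.3.3 (severity), T14.3.4 (serious events) and Table VIII (overview) state no window.

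**The concern.** The question that separates the two regimens is how a second active course is tolerated after a 32-week rest. Of the two windows named for the A versus B comparison, one covers a period of identical treatment by the SAP's own description. In the other, 280 of 365 days precede the point of divergence.

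Patient percentages over the full year therefore mix the period of interest with a long shared period. They also keep in the denominator Safety patients who left before Visit 5 and never received second-course product. A term that a patient already had in the first course cannot be counted again for that patient. A real difference between A and B in the second course could look small, or be absent, in the table that carries the Fisher p-value.

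**Working it through.** **The plan's own figures.** The AE section states no rate or power. The documents do give 46 patients per group and a 23% drop-out rate: 46 / (1 − 0.23) = 59.7, rounded up to 60 per group and 180 in total, as stated. I use 60 for the randomised group and 46 for those who reach the second course.

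**Can the second course be recovered by subtraction?** Taking T14.3.1.1 from T14.3.1.2 leaves Days 142 to 365, which is 224 days:
- Days 142 to 280, off treatment in both groups: 139 days
- Days 281 to 336, second course: 56 days
- Days 337 to 365, follow-up: 29 days

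The second course is 56/224 = 25% of the remainder, so subtraction does not isolate it. For patient counts it also leaves only those whose first occurrence came after Day 141.

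**Recurrence.** Suppose 60 per group, with 12 patients in each group having a term in course 1. In course 2, 3 of those 12 in A and all 12 in B have it again.
- Day 1 to 365 patients: 12 versus 12, Fisher p = 1.00
- Second-course patients: 3 versus 12, Fisher p = 0.025
- Events, at one per recurrence: 12 + 3 = 15 versus 12 + 12 = 24

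The patient count hides the difference and the Events count shows it, without a test and without a second-course window.

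**New events: dilution.** Assumptions: annual background risk b in both groups; 20% of B patients dosed in course 2 gain an event; 46 of 60 per group are dosed; the window is Days 281 to 365 (85 days).
- Full year: A = b; B = 1 − (1 − b)(1 − 0.20 × 46/60)
- Window: A = w = 1 − (1 − b)^(85/365); B = 1 − (1 − w)(0.80)

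Power is for the two-sided Fisher exact test at 5%, by full enumeration.

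| b | Day 1–365, A vs B | Power (60 per group) | Window, A vs B | Power (46 per group) |
|---|---|---|---|---|
| 3% | 3.0% vs 17.9% | 70% | 0.7% vs 20.6% | 88% |
| 5% | 5.0% vs 19.6% | 60% | 1.2% vs 20.9% | 85% |
| 10% | 10.0% vs 23.8% | 43% | 2.4% vs 21.9% | 80% |
| 40% | 40.0% vs 49.2% | 14% | 11.2% vs 29.0% | 47% |

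The first three rows suit a single preferred term; the last suits the any-AE row.

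**Sensitivity of the recurrence case.** Let 15% of both groups react in course 1. The full-year patient table shows 15% versus 15% however many B patients react again. With 46 per group and none in A reacting again, power in the second-course window is 71% if all B reactors recur, 42% if 75% do and 13% if 50% do.

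**The case against.** The strongest reply is that the likeliest signal is already visible. Protocol 7.4 reports that earlier AEs judged possibly related were limited to application site reaction and headache. SAP Appendix B keeps application site reactions out of AE recording unless the investigator decides otherwise, and T14.3.9 tabulates them by visit and group. Protocol 9.5.6 asks at Visit 6 about symptoms since the previous visit, and Visit 5 starts the second course. Visit 6 therefore covers that course and Visit 7 the follow-up, with recurrences recorded afresh. This stands. A reader might infer that the plan gives no view of tolerability in the second course, or that the report would declare A and B alike; the documents do not support either.

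A reader might also infer that recurrence adds nothing to any count, or that every AE table uses the two windows. Neither is so. The Events column in T14.3.1.1 and T14.3.1.2 rises with a recurrence, T14.3.2 to T14.3.4 count events, and those tables and Table VIII state no window.

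The comparison is also exploratory. Fisher testing depends on sufficient data, the A versus B test is optional, and the sample size rests on cure rates. SAP 8.3.1 allows further summaries, and the listings keep the dates. All true, but none of this specifies a second-course table in advance.

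Finally, the power figures depend on their assumptions. Treating all 23% drop-out as occurring before Visit 5, and giving those patients a full year of background risk, enlarges the dilution. The 14% versus 47% contrast belongs to an any-AE background, not to a single term.

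**Conclusion.** The point holds in a limited form. No AE table is confined to onset from the start of the second course, and the full-year patient n(%), presumably the basis of the Fisher p-values, does not register recurrence of a term already counted. The gap concerns AEs other than the graded application site reactions, such as headache, and any local reaction that is also recorded as an AE.

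The loss is moderate at per-term background rates (70% to 43% against 88% to 80%) and larger for any AE (14% against 47%). All AE rates here are assumptions. The A versus B test is also conditional on a significant three-group test, so the chance of reaching and passing it cannot exceed the full-year power shown. The primary efficacy analysis is unaffected. The change is worth making because a stated objective lacks the AE table that addresses it most directly.

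**What to change.** In SAP 8.3.1, add a supplementary table T14.3.1.3 of AEs with onset from the first second-course dose to Visit 7.
- Start the window at the actual dose date, because Visit 5 may fall within 14 days either side of Day 281.
- Use as denominator the Safety patients who received second-course product.
- Count each patient once per preferred term within this window, and keep the Events column.
- Present all three groups, with B versus A as the main contrast.
- Give the relationship and severity summaries for the same window.
- Footnote that the denominator is a post-randomisation subset, so selection is possible, and that B versus C is descriptive because first-course treatment differs.

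The cost is SAP wording and another run of existing table programs. AE start dates are in L16.2.7.1 and Period 2 dose dates in L16.2.5, so no new data are needed. The price is a smaller, selected denominator.
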